6.5.3. Initiation of Nucleos(t)ide Therapy Post GSK3228836 Treatment

Upon cessation of GSK3228836 treatment, participants, regardless of their baseline NA use or not, may experience virological relapse, DNA replication and an ALT flare. Investigators may, at their own discretion and in accordance with local guidelines, decide to initiate new or alternative NA therapy in these participants. Any treatment should be recorded as a concomitant medication.

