4.3. Secondary Endpoint(s) Analyses

4.3.1. Key secondary endpoint(s)

4.3.1.1. Efficacy of GSK3228836 on biomarkers and virus-specific antibody response

The group of estimands supporting the secondary objective of assessing the efficacy of GSK3228836 on biomarkers and virus-specific antibody responses for each sub-population are the population summary for each variable in each treatment arm 1-4.

Missing data for variables defined above (except for Time to ALT normalization) will be ignored, only available data will be summarized. No sensitivity analysis is planned for the group of estimands supporting this objective.

Estimands supporting this objective are defined as follows:

- **Population**: one subpopulation of participants with CHB on stable nucleos(t)ide therapy and a second subpopulation of participants with CHB not currently on nucleos(t)ide therapy. For the time to ALT normalization endpoint, only subjects with ALT>ULN at baseline will be included. For summaries of HBe antibody (anti-HBeAg) levels, only participants who are HBeAg Positive at baseline will be included.
- Treatments: arms 1-4. Estimation within each arm.
- Intercurrent events: For the proportion of participants achieving HBsAg <LLOQ and HBV DNA <LLOQ in the absence of rescue medication at the end of treatment analysis window, end of treatment will be determined using the end of treatment analysis window defined in Section 4.2.2. In line with the primary endpoint, missing data not due to wide disruptive events will be imputed as non-response. Missing data due to wide disruptive events will be ignored without any imputation.

Other endpoints will be summarized regardless of completing IP, interruptions in IP or adherence to IP (treatment policy strategy) and regardless of rescue medication (except

for ALT normalization which can only be achieved in the absence of rescue medication). HBV DNA, HBsAg, HBeAg levels that are below the LLOQ will be imputed for summaries of actual values and change from baseline following the rules in Section 4.1.1.

1) Categorical Variables:

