- Achieving HBsAg <LLOQ and HBV DNA <LLOQ at the end of treatment analysis window. Data will be presented overall and by baseline stratification factors (HBsAg <3 log IU/mL and Negative HBeAg; BsAg >3 log IU/mL and Negative HBeAg; HBsAg <3 log IU/mL and Positive HBeAg; HBsAg >3 log IU/mL and Positive HBeAg; HBsAg <3 log IU/mL and All HBeAg; All HBsAg and Negative HBeAg; HBsAg <3 log IU/mL and All HBeAg; All HBsAg and Positive HBeAg)
- Categorical changes from baseline in HBsAg (e.g., <0.5, ≥0.5, ≥1, ≥1.5, ≥3 log₁₀ IU/mL) and in HBV DNA (e.g., <1, ≥1, ≥2, ≥3 log IU/mL). Change from baseline will be presented at each visit and for the following time periods: up to and including Week 6, Up to and including Week 12, Up to and including Week 24, Up to and including off-treatment Week 24. Data will be presented overall and by baseline stratification factors (HBsAg <3 log IU/mL and Negative HBeAg; BsAg >3 log IU/mL and Negative HBeAg; HBsAg >3 log IU/mL and Positive HBeAg; HBsAg >3 log IU/mL and All HBeAg; All HBsAg and Negative HBeAg; HBsAg <3 log IU/mL and All HBeAg; All HBsAg and Positive HBeAg)
- ALT normalization (ALT \leq ULN) over time in absence of rescue medication in participants with baseline ALT \rightarrow ULN
- HBe antibody (anti-HBeAg) levels in HBeAg Positive patients
- HBs antibody (anti-HBsAg) levels (HBs Antibody >=11.5 IU/L is HBs antibody positive and HBs Antibody <11.5 IU/L is HBs antibody negative)
- **Population summary:** proportion of participants in each category for each treatment arm.

2) Continuous Variables:

- Actual values and change from baseline over time of HBsAg and HBV DNA
- Actual values and change from baseline of HBeAg levels
- HBs antibody (anti-HBsAg) levels
- **Population summary**: mean values and mean changes from baseline for each variable in each treatment arm.

3) Time to Event Variable:

- Time to ALT normalization in absence of rescue medication in participants with baseline ALT>ULN.
- **Population summary**: Turnbull's estimator for the non-parametric estimation of time to ALT normalization in each treatment arm.

ALT normalization is defined in subjects with ALT>ULN at baseline as a return to ≤ULN (ULN = 40 for males and 33 in females). Time to ALT normalization is defined as time from baseline to the first follow-up where subject's ALT has returned to normal.

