For participants who withdraw from the study or Participants with ALT>ULN at the end of study, time to ALT normalization will be censored at the time of last visit with non-missing ALT value available. Participants who receive rescue medication cannot go on to achieve the event of 'ALT normalization in the absence of rescue medication'; such participants will be censored at the end of the follow up period.

4.3.1.2. Comparison of efficacy between arms 1, 2 and 3

Definition of Estimands

Estimands supporting secondary objective of comparing the efficacy between arms 1, 2, and 3 are defined as follows:

- **Population**: separate assessment for the following:
 - participants with CHB on stable nucleos(t)ide therapy
 - participants with CHB not currently on nucleos(t)ide therapy
- Variable: Sustained virologic response (SVR) for 24 weeks after the end of GSK3228836 treatment in the absence of rescue medication.
- **Treatments**: arms 1, 2, and 3. Three treatment comparisons between: arms 1 and 2, arms 1 and 3, and arms 2 and 3.
- **Intercurrent events**: use of rescue medication, and discontinuation of/interruption of/adherence to IP. The use of rescue medication has been incorporated into the definition of variable (composite strategy). Discontinuation of, interruption of, and adherence to IP will be ignored (treatment policy). Wide disruptive events (such as COVID-19 pandemic) leading to discontinuation of, interruption of, and non-adherence to GSK3228836 will be handled assuming they had not happened (hypothetical strategy).
- **Population summary**: difference in proportion of participants who achieve SVR between treatment arms.

The group of estimands supporting this objective for each sub-population are the difference in each treatment comparisons in the proportion of participants who achieve SVR for 24 weeks after the end of GSK3228836 treatment in the absence of rescue medication regardless of completing IP, interruptions in IP or adherence to IP had they not been affected by wide disruptive events.

The non-responder imputation described in Section 4.2.2 will be used when HBsAg and HBV DNA data are missing from visits required to derive the endpoint.

Main analytical approach

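### The censoring sentence for time to ALT normalization in SAP 4.3.1.1 is not limited to participants who never normalized, so applied literally it removes first-normalization events

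*SAP*

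**What the plan says.** The relevant text is the Time to Event Variable part of SAP 4.3.1.1.

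- **Who is analysed:** "For the time to ALT normalization endpoint, only subjects with ALT>ULN at baseline will be included".
- **What counts as the event:** "ALT normalization is defined in subjects with ALT>ULN at baseline as a return to ≤ULN". No confirmatory value and no minimum duration are required.
- **When the event occurs:** "Time to ALT normalization is defined as time from baseline to the first follow-up where subject's ALT has returned to normal".
- **Who is censored:** the sentence opens with participants who withdraw from the study and continues: "Participants with ALT>ULN at the end of study, time to ALT normalization will be censored at the time of last visit". The censoring time is the last visit that has an ALT value.
- **Rescue medication:** participants who take it are described as unable, from then on, to reach the event, and "such participants will be censored at the end of the follow up period".
- **Estimator:** Turnbull, separately in each arm. No sensitivity analysis is planned for this group of estimands.

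Protocol 9.4.4.1 names the same endpoint and has almost the same censoring sentence, without the requirement that ALT be available at the last visit. It does not define the event time as the first normal follow-up, and it leaves further detail to the analysis plan.

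**The concern.** The event rule looks at the first normal value and ignores what follows. The censoring rule looks at the participant's state later on: withdrawn, or above ULN at the end. The two overlap for anyone who normalizes and then either rebounds by study end or leaves the study. Nothing in SAP 4.3.1.1 says which rule wins.

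The overlap is foreseeable. Protocol 6.5.3 warns that after treatment stops participants "may experience virological relapse, DNA replication and an ALT flare". The withdrawal part needs no flare at all: a participant who normalizes during treatment and later leaves the study is enough.

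If the censoring sentence is given priority, events already observed are removed because of information that arises after them. The curve then describes something close to having normalized, stayed in the study and still been normal at the end. That is a different quantity from time to first normalization, and a lower one.

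**Working it through.** The documents give no event count, precision or assumed rate for this endpoint, so there is no planned figure to reproduce. The check has two parts.

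**1. Applying both rules to single records.**

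| Record (baseline ALT>ULN) | Event rule | Censoring sentence, literally |
|---|---|---|
| ALT ≤ULN at Day 57, >ULN at Day 330 | Event at Day 57 | Censored at Day 330 |
| ALT ≤ULN at Day 57, withdraws at Day 120 | Event at Day 57 | Censored at about Day 120 |

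Each record receives two incompatible outcomes. Turnbull's estimator needs either a finite interval or right-censoring for each participant, so the programmer has to choose.

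**2. Size of the difference if the censoring sentence wins.** Let p be the proportion who ever normalize, f the proportion of normalizers above ULN at study end, and w the proportion who withdraw. All three are assumptions. Under the literal rule an event survives only if the participant normalizes, does not rebound and does not withdraw. The crude event proportion is therefore p(1−f)(1−w). Withdrawers leave the risk set without an event, so in large samples the product-limit estimate lies between p(1−f)(1−w) and p(1−f). For p = 0.60:

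- f = 0.10, w = 0.05: 0.60 × 0.90 × 0.95 = 0.513, upper limit 0.60 × 0.90 = 0.540
- f = 0.30, w = 0.10: 0.60 × 0.70 × 0.90 = 0.378, upper limit 0.60 × 0.70 = 0.420
- f = 0.50, w = 0.10: 0.60 × 0.50 × 0.90 = 0.270, upper limit 0.60 × 0.50 = 0.300

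A simulation scored the same 20,000 records per scenario both ways. It used the protocol visit days, normalization spread evenly over the visits from Day 8 to Day 169, and withdrawal spread evenly over all visits. A product-limit estimate at Day 330 stood in for Turnbull.

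| p | f | w | First event counted | Censoring sentence given priority | Normalizers meeting both rules |
|---|---|---|---|---|---|
| 0.60 | 0.10 | 0.05 | 0.596 | 0.523 | 12.8% |
| 0.60 | 0.10 | 0.10 | 0.601 | 0.510 | 16.1% |
| 0.60 | 0.30 | 0.05 | 0.599 | 0.405 | 32.6% |
| 0.60 | 0.30 | 0.10 | 0.602 | 0.398 | 34.5% |
| 0.60 | 0.50 | 0.05 | 0.593 | 0.287 | 51.6% |
| 0.60 | 0.50 | 0.10 | 0.603 | 0.285 | 53.0% |
| 0.40 | 0.10 | 0.05 | 0.403 | 0.352 | 13.1% |
| 0.40 | 0.10 | 0.10 | 0.403 | 0.344 | 15.3% |
| 0.40 | 0.30 | 0.05 | 0.403 | 0.273 | 32.5% |
| 0.40 | 0.30 | 0.10 | 0.402 | 0.263 | 34.7% |
| 0.40 | 0.50 | 0.05 | 0.396 | 0.190 | 52.0% |
| 0.40 | 0.50 | 0.10 | 0.398 | 0.188 | 53.0% |

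The results for p = 0.60 lie within the limits above. The gap between the two codings runs from 0.403 − 0.352 = 0.051 to 0.603 − 0.285 = 0.318, that is, about 5 to 32 percentage points.

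For scale, suppose 30 participants in an arm had raised baseline ALT (an assumption; the documents do not say). The standard error of a 60% estimate would be √(0.60 × 0.40 / 30) = 0.089. The gap at 10% rebound, 0.073 to 0.091, is then about one standard error.

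**The case against.** The strongest reply is convention. In a time-to-first-event analysis, censoring is for participants without an event, and most programmers would count the first normalization and apply the censoring sentence only to the rest. Read that way there is no conflict and no bias. This is a fair expectation of practice, but the sentence as written says otherwise and no priority rule backs the conventional reading.

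Other replies limit the point and stand:

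- **Rescue medication.** A reader might infer that the rescue sentence also cancels a normalization reached before rescue. The text does not support that. It says such participants cannot go on to reach the event, which looks forward from the start of rescue. It would be clearer if stated, but it is not a contradiction.
- **The protocol.** A reader might infer the same contradiction in Protocol 9.4.4.1. That section has no first-follow-up rule for its censoring sentence to contradict.
- **Frequency.** A reader might infer that transient normalizers will be common. Protocol 6.5.3 says only that a flare may happen, and neither document gives a rate for normalized ALT returning above ULN by study end.
- **Consequence.** The estimate is descriptive and within arm, with no test or decision rule attached. SAP 4.3.1.1 also reports the proportion with normal ALT over time, and that summary is not subject to this time-to-event censoring rule.

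**Conclusion.** The point holds as a defect in a stated SAP rule. Followed literally, the withdrawal and end-of-study censoring sentence can only remove first-normalization events, so the curve is biased downward for the estimand defined just before it. That direction is general. The size is not known: with 60% truly normalizing, 5–10% withdrawing and 10–50% rebounding, the Day 330 estimate would be about 0.52 down to 0.285. If the first event is counted regardless, the effect is nil.

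Two stronger conclusions may tempt a reader. One is that the reported curve will be wrong; the documents do not show how the rule will be coded. The other is that comparisons between arms will be distorted. Arm 3 stops active drug at Week 12 and so has about 12 weeks longer off drug by study end than Arms 1, 2 and 4, which makes unequal loss of events conceivable under literal coding. But the documents give no rebound rates by arm, and the endpoint is planned as estimation within each arm.

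SVR, the sample size and the regimen selection rules do not use this endpoint and are unaffected.

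**What to change.** Replace the censoring text in SAP 4.3.1.1 with wording such as:

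*Participants with no post-baseline ALT ≤ULN before any rescue medication are censored at the last visit with non-missing ALT (or at the end of the follow-up period if they received rescue medication). An earlier normalization counts as an event regardless of later ALT, rescue or withdrawal.*

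This also makes the forward-looking sense of the rescue sentence explicit. Aligning the censoring sentence in Protocol 9.4.4.1 is optional.

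If sustained normalization was intended, the event definition in SAP 4.3.1.1 should be changed instead, with the required duration or confirmation stated.

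The cost is a short text edit in the SAP. No new data, visits or analyses are needed.

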4.3.2. Supportive secondary endpoint(s)

Historical placebo control

If historical individual patient-level data are available, a longitudinal model including historical response at 12, 24 and 48 weeks of placebo treatment will be constructed. For the first 12-week period, the model will allow dynamic borrowing from historical placebo data to the concurrent placebo in Weeks 1-12 in arm 4. Furthermore, the model will provide longitudinal prediction of response at Week 24 and Week 48 for participants in arm 4 (had they continued on Placebo rather than switching to GSK3228836 treatment).

4.3.3. Pharmacokinetic Secondary Endpoints

4.3.3.1. Endpoint / Variables

Pharmacokinetics (PK) of GSK3228836 and nucleos(t)ide will be characterized. In all participants, GSK3228836 $C\tau$ and terminal half-life (t½) will be estimated. In participants with intensive PK sampling, GSK3228836 and nucleos(t)ide plasma PK parameters will be derived, including but not limited to AUC, $C\tau$, Cmax and tmax.

4.3.3.2. Derived Pharmacokinetic Parameters

Pharmacokinetic parameters will be calculated by standard non-compartmental analysis using the currently supported version of WinNonlin. All calculations of non-compartmental parameters will be based on actual sampling times. Pharmacokinetic

parameters listed will be determined from the plasma concentration-time data, as data permits.

Table 6 Pharmacokinetic Parameters and Parameter Description

Parameter	Data	Analyte	Parameter Description
AUC(0-24)	Intensive PK	GSK3228836 Nucleos(t)ide	Area under the concentration-time curve from time zero up to 24 hours post-dose.
AUC(0-168)	Intensive PK	GSK3228836	Area under the concentration-time curve from time zero up to 168 hours post-dose.
Сτ	Intensive PK	Nucleos(t)ide	Concentration at the end of the dosing interval
Сτ	Sparse PK – All Subjects	GSK3228836	Concentration at the end of the dosing interval
Cmax	Intensive PK	GSK3228836 Nucleos(t)ide	Maximum observed concentration
tmax	Intensive PK	GSK3228836 Nucleos(t)ide	Time of maximum observed concentration
t½	Sparse PK – All Subjects	GSK3228836	Terminal half-life determined using concentrations collected during the off-treatment period

Sparse PK is collected weekly during the dosing period and at certain pre-specified visits during the off-treatment period. Intensive PK is collected at one visit between Week 14 (inclusive) and week 24 (inclusive).

4.3.3.3. Population of Interest

The secondary pharmacokinetic analyses will be based on the Pharmacokinetic (PK) population, unless otherwise specified.

4.3.3.4. Statistical Analyses / Methods

Unless otherwise specified, endpoints / variables defined in Table 6 will be summarised using descriptive statistics, graphically presented (where appropriate) and listed. Descriptive statistics for continuous variables will summarise n, arithmetic mean, SD, 95% CI, median, minimum, maximum, geometric mean with associated 95% CI, and the between-participant CV (%CVb) for the geometric mean. For sparse PK summary of $C\tau$ and t1/2, additionally present 5th and 95th percentile.

Sparse PK parameters ($C\tau$ and t1/2) of GSK3228836 will be summarised and listed by treatment arm, study visit (only applies to $C\tau$), geographic region (All participants, China, Japan and East Asia). Sparse $C\tau$ -time plots will be created and compared by the same factors.

Intensive PK parameters (AUC(0-24), AUC(0-168), Cmax and tmax) of GSK3228836 will be summarised and listed by dose level (150mg and 300mg). Intensive concentration-time plots will be created and compared by the same factors.

Intensive PK parameters (AUC(0-24), $C\tau$, Cmax and tmax) of nucleos(t)ide will be summarised and listed separately for tenofovir (separately for tenofovir disoproxil fumarate and tenofovir alafenamide) and entecavir. Intensive concentration-time plots will be created separately for tenofovir (separately for tenofovir disoproxil fumarate and tenofovir alafenamide) and entecavir.

Refer to Section 4.6 for more information on geographic region subpopulations.

4.4. Exploratory Endpoints Analyses

4.4.1. Exploratory Efficacy Endpoints

In addition to the exploratory analyses described in this section, all primary and secondary endpoints assessed for Arms 1, 2, and 3 will also be assessed as exploratory analyses in Arm 4.

4.4.1.1. Comparison of efficacy between 12 weeks of GSK3228836 treatment with a loading dose or without a loading dose

Estimands supporting exploratory objective of comparing the efficacy between 12 weeks of GSK3228836 treatment with a loading dose or without a loading dose are defined as follows:

- **Population**: separate assessment for the following:
 - participants with CHB on stable nucleos(t)ide therapy.
 - participants with CHB not currently on nucleos(t)ide therapy.
- **Variable**: Sustained virologic response (SVR) for 24 weeks after the end of GSK3228836 treatment in the absence of rescue medication.
- Treatments: arm 3 and 4. Treatment comparison between arms 3 and 4.
- Intercurrent events: use of rescue medication, and discontinuation of/interruption of/adherence to IP. The use of rescue medication has been incorporated into the definition of variable (composite strategy). Discontinuation of, interruption of, and adherence to IP will be ignored (treatment policy). Wide disruptive events (such as COVID-19 pandemic) leading to discontinuation of, interruption of, and non-adherence to GSK3228836 will be handled assuming they had not happened (hypothetical strategy).
- **Population summary**: difference in proportion of participants who achieve SVR between treatment arms 3 and 4.

The group of estimands supporting this objective for each sub-population are the differences between arms 3 and 4 in the proportion of participants who achieve SVR for 24 weeks after the end of GSK3228836 treatment in the absence of rescue medication regardless of completing IP, interruptions in IP or adherence to IP had they not been affected by wide disruptive events.

The non-responder imputation described in Section 4.2.2 will be used when HBsAg and HBV DNA data are missing from visits required to derive the endpoint.

Comparisons between arms will be made by calculating differences between the posterior distributions of the response rate in each arm which will be summarised to obtain posterior

209668

means and CIs. Samples from the posterior distribution of the response rates in each arm will also be used to obtain posterior probabilities of interest (e.g. $Pr(Arm\ 1 - Arm\ 2 > -5\%\ |\ Data)$). The point estimates of differences in sustained virologic response rate with 95% credible intervals will be calculated for the treatment comparisons described in the estimands.

4.4.1.2. Concordance of virologic response at Week 6, Week 12 and Week 24 and achieving SVR

The concordance of virologic response (HBV DNA < LLOQ and HBsAg < LLOQ) at ontreatment timepoints of interest with achieving SVR will be explored. Number of subjects with an early response (Yes or No) will be cross tabulated with SVR (Yes or No) for ontreatment visits Week 6, Week 12 and Week 24 separately. Positive Predictive Value and Negative Predictive Value will be presented.

4.4.1.3. Pharmacodynamic effect of GSK3228836 on exploratory biomarkers

The pharmacodynamic effect of GSK3228836 on exploratory biomarkers (HBcrAg, HBV RNA) will be assessed.

Summary tables and figures will be created to show HBcrAg and HBV RNA (for units copies/mL and log10 copies/mL) over time. Additionally, summaries of HBcrAg by HBeAg status, and HBV RNA for RoW (excluding China) and China population will be presented.

For end of treatment visit only, a summary of HBcrAg and HBV RNA for subjects with/or without HBsAg < LLOQ at end of treatment will be presented, by SVR status.

Further details will be described in a separate PK-PD analysis plan developed by CPMS.

4.4.2. Exploratory PK-PD Endpoints

To evaluate PK-efficacy relationship and PK-safety relationship, exploratory graphical analyses will be initially performed for efficacy (e.g., HBsAg) and safety endpoints. If a relationship between exposure and efficacy and/or safety endpoints is present, population PK-PD modelling will be conducted using nonlinear mixed effect methods.

The model will assess the effect of various factors (covariates) of the modelled efficacy or safety endpoints. Relevant PK-PD model endpoints for example:

- apparent clearance
- apparent volume of distribution
- IC50
- random variability

Full details of PK-PD and Population PK analysis will be described in a separate analysis plan developed by CPMS.

